## 5.2 REPORTING PROCEDURES

All adverse events should be reported. Depending on the nature of the event the reporting procedures below should be followed. Any questions concerning adverse event reporting should be directed to the Chief Investigator in the first instance.

### 5.2.1 Non-serious AEs

All such events, whether expected or not, should be recorded.

### 5.2.2 Serious AEs

An SAE form should be completed and faxed to the Chief Investigator within 24 hours. However, hospitalisations for elective treatment of a pre-existing condition do not need reporting as SAEs.

All SAEs should be reported to the West of Scotland (REC 5) where in the opinion of the Chief Investigator, the event was:

- 'related', ie resulted from the administration of any of the research procedures; and
- 'unexpected', ie an event that is not listed in the protocol as an expected occurrence

Reports of related and unexpected SAEs should be submitted within 15 days of the Chief Investigator becoming aware of the event, using the NRES SAE form for non-IMP studies. The Chief Investigator must also notify the Sponsor of all related and unexpected SAEs.

Local investigators should report any SAEs as required by their Local Research Ethics Committee, Sponsor and/or Research & Development Office.

## 6. ASSESSMENT & FOLLOW UP

Patients will be followed up over a 3 month period remotely while wearing their ambulatory ECG. 12-lead ECG and UHF-ECG data will be collected at the index visit. Symptom diaries and ambulatory ECG recordings will be collected at the end of the study interval. Any incidental findings that we identify during the study will be reviewed by the research team and reported to the GP and also the cardiology team normally looking after the patient. We will continue to follow up all patients after their last contact with the research team through review of the electronic health record and any clinical cardiac device checks up until the end of the study on 1st April 2027, at which time all follow up will cease. The prospective studies

will end after 200 patients have undergone the 3 month interval of follow up or by the study end date of 1st April 2027.

## **7. STATISTICS AND DATA ANALYSIS**

We expect to have access to over 3000 patients' worth of ECG data to train and validate our neural networks, comprising a similar proportion of Brugada and non-Brugada ECGs. Our group has published extensively regarding applications of AI to ECG data (13–17) and includes experienced, independently-funded clinician scientists and engineers with expertise in machine learning. They will guide me in developing neural networks for ECG classification tasks and signal processing. As we will be employing a very similar methodology to our previous successful ECG AI projects in this experiment, we are confident that this quantity of ECG data will be sufficient to develop highly accurate neural networks.

The accuracy of the prolonged duration ambulatory ECG recordings will be calculated using a binomial distribution. Assuming an actual accuracy of 95% and a target accuracy of >85% for ECG analysis discriminating between healthy normal participants and manifest Brugada patients, 90 patients will provide greater than 80% power in demonstrating that the measured accuracy is significantly greater than 85% at the two-tailed 5% significance level. To achieve 90 patients with some loss to follow up, I will recruit 50 healthy volunteers and 50 manifest Brugada patients.

McNemar's test will be used for paired analysis of 24-hour 12 lead Holter and prolonged ambulatory ECG recordings in the concealed arrhythmia patient set. Historical data report 20 to 34% sensitivity for 24-hour Holter for detection of the Brugada ECG pattern in patients with concealed Brugada syndrome (5,6). Assuming 25% sensitivity for 24-hour Holter and 60% for prolonged ambulatory ECG recordings beyond 24 hours, with the prolonged ambulatory ECG recordings being able to identify 80% of 24-hour Holter-identified cases, 35 patients would be needed to provide 90% power at the 5% significance level. I will recruit 50 patients.

We are also seeking to identify at least one extra patient with Long QT or Brugada syndrome by performing extended duration monitoring beyond standard 12 lead 24-hour Holter. Registry data (7–9) suggests that between 3–4% of idiopathic VF patients eventually receive a specific diagnosis of Brugada syndrome through conventional diagnostic testing and routine clinical follow up. A similar proportion are diagnosed with long QT syndrome. If extended duration monitoring can identify half of these (4%), then 50 patients will provide 87% power to detect at least one extra case (simulated through repeat sampling of a binomial distribution).

We also plan to recruit 100 patients with other inherited arrhythmic conditions, who can be subdivided into high and low arrhythmic risk groups. We believe that these cohort sizes will be adequate to gather sufficient pilot data to enable identification of subtle changes in UHF-ECG profiles.

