### Study B: Remote arrhythmia diagnostics

In this study, we will undertake validation studies to assess the robustness, accuracy and applicability of the aforementioned AI algorithms (i.e. neural networks) on ECG recordings from several different ambulatory monitoring modalities. This protocol will encompass participants recruited in Groups A-C.

Commented [KS1]: Added for clarity

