### Protocol

Participants will undergo the consent process and testing during a single research visit. The steps will include the following:

- Participants will be counselled regarding the research study and written informed consent will be obtained.
- All participants will undergo a 12-lead ECG and ultra-high-frequency ECG recording.
- Group A participants will additionally undergo an echocardiogram to ensure that they have a structurally and electrically normal heart.
- All participants will undergo testing with different ambulatory ECG modalities, depending on availability and resources. This will include Holter monitoring up to 12 leads, wearable cardiac monitoring devices (namely the Boston Scientific BodyGuardian MINI) and other wearable ECG technologies. These devices will be fitted by a member of the research team.
- Participants will be instructed how to maintain continuous ambulatory ECG recording via their device as far as possible, including during day-to-day life and including during sleep. Provisions of additional adhesive patches and devices may be required to facilitate long term monitoring up to 3 months.
- Participants will be provided with a digital symptom and activity diary via email to record their daily activity diary, the occurrence of any arrhythmia-related symptoms and gather real-time feedback on tolerability of their monitoring device. In patients who do not have an email, a paper symptom/activity diary will be provided.
- Data will be remotely uploaded onto the cloud via secure digital infrastructure or housed securely on the cardiac monitoring device.
- Participants will be provided with pre-paid parcels with courier collection for retrieval of the ambulatory ECG devices and wearable ECGs at the end of the 3 month study period.

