### Application of ECG AI to ECG recordings

ECG recordings will be downloaded onto local storage. The digital ECGs will be processed and denoised using specialized algorithms developed by the research team. The previously developed ECG AI algorithms for Brugada syndrome will subsequently be applied to the cleaned ECG recordings for all patient groups.

We will establish the sensitivity for the Brugada classification algorithms on recordings from patients with manifest Brugada syndrome (Group C) and their specificity using the recordings from the healthy volunteers (Group A). The algorithms will also be applied to

patients with concealed arrhythmia syndromes (Group B) to determine the diagnostic yield of different ambulatory ECG recording modalities for different time durations. We will apply both the in-house developed Brugada ECG AI algorithms as well as existing ECG AI algorithms developed by external academic or industry collaborators, to investigate for underlying concealed arrhythmias.

**Commented [BK2]:** From this description I think this should be a Pre-clinical device development or performance testing medical device study (no MHRA review required)

**Commented [KS3R2]:** I have amended project filter q2 on IRAS to reflect

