#### Primary Outcome Measures

- Sensitivity, specificity and AUC value for neural networks 1 and 2 to detect the Brugada ECG pattern in 12-lead ECGs.

- Yield of extended duration ambulatory ECG monitoring to detect the Brugada ECG pattern in patients with concealed Brugada syndrome, using neural networks 1 and 2.
- Sensitivity, specificity and AUC value for neural network 3 to diagnose concealed Brugada syndrome from 12-lead ECGs
- Sensitivity, specificity and AUC value for neural network 4 to diagnose an SCN5a mutation from 12-lead ECGs.
- Yield of extended duration ambulatory ECG monitoring to detect the Brugada ECG pattern (neural networks 1 and 2) and LQTS manifestation in patients with idiopathic VF.

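### Does the 85% accuracy test in Study B need its network and device named in the protocol before its power can be trusted?

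*Protocol*

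**What the plan says.** Section 7 of the protocol begins: "The accuracy of the prolonged duration ambulatory ECG recordings will be calculated using a binomial distribution". It takes a true accuracy of 95% and a target above 85% for separating healthy volunteers from manifest Brugada patients, at the two-tailed 5% level, and states that "90 patients will provide greater than 80% power in demonstrating that the measured accuracy is significantly greater than 85" per cent. To allow for losses, "I will recruit 50 healthy volunteers and 50 manifest Brugada patients". No network or device is named.

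Study B (section 3.3) is to validate the algorithms on "ECG recordings from several different ambulatory monitoring modalities". Its protocol subsection says: "All participants will undergo testing with different ambulatory ECG modalities, depending on availability and resources". It goes on: "This will include Holter monitoring up to 12 leads, wearable cardiac monitoring devices (namely the Boston Scientific BodyGuardian MINI) and other wearable ECG technologies". The subsection on applying the ECG AI commits to sensitivity in manifest Brugada patients (Group C) and specificity in healthy volunteers (Group A), for algorithms in the plural. It adds that external algorithms will also be applied.

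The first primary outcome in section 3.4 is "Sensitivity, specificity and AUC value for neural networks 1 and 2 to detect the Brugada ECG pattern in 12-lead ECGs". For ambulatory recordings, section 3.4 lists only yield, in concealed Brugada syndrome and idiopathic VF. The study summary also lists algorithm sensitivity, specificity and AUC on ECGs from a 12-lead vest, a device mentioned nowhere else.

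**The concern.** A power statement belongs to one defined quantity. Here several could be meant. Appendix 2 has two networks that classify the Brugada pattern (NN1 and NN2), and Study B names three kinds of device (Holter, the BodyGuardian MINI, other wearables). Read literally, that gives 2 × 3 = 6 accuracies, and section 7 does not say which is held against 85%.

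Two harms could follow. If the network and device were picked after the results were seen, the chance of a false pass would rise. And since devices are supplied as resources allow, no single device is assured 90 wearers, so the power could fall below the stated figure. The outcome lists do not settle the matter: overall accuracy is not in section 3.4, and the summary's nearest entry concerns a vest.

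**Working it through.** **Inputs.** From section 7: null accuracy 0.85, true accuracy 0.95, n = 90, two-sided 5% (0.025 in the upper tail), 50 + 50 recruited. The counts of networks and devices come from Appendix 2 and section 3.3. Device coverage and correlation between results are assumptions, because the protocol gives neither.

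**1. The plan's own figure.** Reject when X ≥ c, with c the smallest count for which P(X ≥ c | n, 0.85) ≤ 0.025.
- n = 90: c = 84, P(X ≥ 84 | 0.85) = 0.0131, power P(X ≥ 84 | 0.95) = 0.836.
- Normal approximation: Φ[(0.10 − 1.96·√(0.85·0.15/90)) / √(0.95·0.05/90)] = Φ[(0.10 − 0.0738)/0.0230] = 0.873.

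Both agree with the claim of more than 80%.

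**2. How many people are needed.** Exact power is not monotone in n, because the cut-off moves in whole counts.

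| Usable n | Cut-off | Power |
|---|---|---|
| 100 | 93 | 87.2% |
| 90 | 84 | 83.6% |
| 84 | 78 | 87.3% |
| 83 | 78 | 76.5% |
| 79 | 74 | 79.7% |
| 78 | 73 | 80.5% |
| 75 | 70 | 82.8% |
| 74 | 70 | 68.9% |
| 60 | 57 | 64.7% |
| 50 | 48 | 54.1% |
| 30 | 30 | 21.5% |

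From 84 to 100 usable participants power stays above 80%. From 79 to 83 it lies between 76.5% and 79.7%, and from 75 to 78 it is again above 80%. A real loss of power therefore needs fewer than 75 of the 100 recruited to have a usable result. If each participant contributes one result from whatever prolonged recording was worn, device supply alone does not bring n that low. If the 90 were split into three device groups of 30 and each tested separately, power would be 21.5%, but the protocol plans no such split test.

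**3. False passes if several accuracies were tested unadjusted at true 85%.**
- Two (NN1 and NN2 on the same recordings): at most 2 × 0.0131 = 0.026 under any dependence.
- Six, independent: 1 − (1 − 0.0131)^6 ≈ 0.076.
- Six, with a within-person latent correlation of 0.9 (simulation): 0.049.

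The nominal upper tail is 0.025. A single test attains 0.013 only because counts are whole numbers, so comparing with 0.013 exaggerates the rise.

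**4. A true accuracy of 88%.** One named pair passes 7.4% of the time, and at least one of six passes 21% (correlation 0.9) to 37% (independent). This is not an error rate. If the truth is 88%, concluding that accuracy exceeds 85% is correct.

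**5. Link to the listed measures.** With 45 per group, accuracy = (sensitivity + specificity)/2. Both components are promised in section 3.3 for the same two groups, so reporting them yields the powered accuracy.

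**The case for a change.** The strongest contrary case is that the protocol states the hypothesis and sample size itself, so the powered quantity should appear in its own outcome list. An analysis plan cannot arrange for enough people to wear a given device; that has to be settled during recruitment. The protocol also expects, under burdens and risks in section 3.3, that devices will not always be worn. And two networks on one device already leave a choice: a Bonferroni split over two tests moves the cut-off to 85 of 90 and lowers power to 70.5%. Overall accuracy can also hide imbalance: 84 of 90 correct allows six misses, and if all fell in the Brugada group sensitivity would be 39/45 = 86.7%.

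Part of this stands. Section 3.4 does omit the Group A versus Group C ambulatory comparison that section 7 powers, and the summary's vest does not match the devices named in section 3.3. The rest carries less weight.
- Section 7 refers to the prolonged recordings collectively, and pooling to one result per participant is a natural reading.
- The 24-hour 12-lead Holter is the comparator in the McNemar analysis, so it may not count as a prolonged recording. Six is then not a minimum.
- The two harms do not occur together as calculated. The six-pair error rates give all 90 people to every pair, while the power losses assume that devices do not reach 90.
- With two networks the unadjusted error is already at the nominal level, so the Bonferroni penalty need not be paid.
- Imbalance would show, because sensitivity and specificity are to be estimated separately.

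**Conclusion.** The concern calls for no change. The stated power is correct (83.6% exact), and section 7 fixes what a protocol needs for this test: who is compared, on what kind of recording, against which threshold, at what level and with how many people. The choice of network, and the rule that turns up to three months of recording into one correct or incorrect result per person, are gaps that analysts ordinarily fill in the analysis plan before the recordings are analysed. Their absence from the protocol does not show that they are undecided.

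On the most direct reading (pooled recordings, NN1 and NN2) the excess error is about 0.1 percentage point at most, 2.6% against 2.5%. Reaching 4.9% to 7.6% requires six separately tested pairs. Power well below 80% requires fewer than 75 usable participants out of 100. Both are assumptions, not statements in the protocol. Making one device compulsory for these 100 people would be an operational trade-off in a proof-of-concept study meant to try several modalities.

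The mismatch between the outcome lists is a clerical slip. Aligning them would be tidier but would change no estimate, because the sensitivity and specificity that make up the accuracy are already committed to in section 3.3. This conclusion assumes one result per participant and a network chosen before the results are seen.

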## STUDY SUMMARY

TITLE	Unmasking Concealed Arrhythmia Syndromes
DESIGN	Proof-of-concept studies to develop ECG AI algorithms, followed by case-control diagnostic accuracy study and prospective cohort studies
AIMS	
 
1. To develop machine learning algorithms for 12-lead ECGs to detect diagnostic features of Brugada syndrome.
 
2. To test and validate these algorithms prospectively in participants wearing ambulatory ECG recording devices.
 
3. To ascertain the role of UHF-ECG for risk stratification in patients with inherited arrhythmogenic conditions
 

OUTCOME MEASURES	
 
• Brugada ECG algorithm sensitivity, specificity and AUC value for both 12 lead ECGs and 12 lead vest ECGs
 
• Yield of extended duration multi-electrode ambulatory ECG monitoring to detect the Brugada ECG pattern in concealed Brugada syndrome
 
• The utility of extended duration multi-electrode ambulatory ECG monitoring to detect a single case of underlying Brugada or LQTS manifestation in idiopathic VF
 

POPULATION	Healthy volunteer controls, patients with a diagnosis of Brugada syndrome, patients with a diagnosis of idiopathic VF syndrome and patients with other inherited arrhythmogenic conditions
ELIGIBILITY	
Participant sets (Appendix 1):
 
 
• Group A – healthy volunteers
 
• Group B – concealed arrhythmia syndrome patients (patients with a normal ECG with a known underlying arrhythmic diagnosis)
 
• Group C – manifest arrhythmia syndrome patients (patients with an arrhythmic syndrome with an abnormal ECG)
 

DURATION	November 2023 – November 2026 (3 years)

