### **Prospective studies**

200 patients will be recruited in total. The direct care team will screen the records and identify patients followed up at Imperial College Healthcare Trust that are suitable for the study. Patients will also be identified at several national ICC centres, via our collaborators, and invited to attend the Imperial College London Pert Rose Research Unit for recruitment into our study.

We will recruit 3 groups of participants:

- Group A – healthy volunteers
- Group B – patients with a normal ECG and an underlying inherited arrhythmic syndrome
- Group C – patients with an arrhythmic syndrome with an abnormal ECG

We will be aiming for an approximately even distribution of participants to be recruited to each group.

The direct care team will obtain consent to share their information with the research care team. Once the patient has consented to their information being shared, a member of the research team will contact the patient and explain the details of the research study. Written consent will be gained prior to any tests taking place.

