## 12. APPENDICES

### Appendix 1 – Arrhythmic syndromes

#### Group B (concealed arrhythmia syndromes):

- Concealed Brugada syndrome
- Early repolarisation syndrome
- Idiopathic VF
- Purkinje-related arrhythmic syndrome
- Concealed pre-excitation

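### McNemar's test is assigned to the whole concealed-arrhythmia group, but its inputs, its N of 35 and the matching primary outcome concern concealed Brugada syndrome only

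*Protocol*

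**What the plan says.** Section 7 assigns McNemar's test to the "paired analysis of 24-hour 12 lead Holter and prolonged ambulatory ECG recordings in the concealed arrhythmia patient set". The Study Summary defines that group as "Group B – concealed arrhythmia syndrome patients (patients with a normal ECG with a known underlying arrhythmic diagnosis", and Appendix 1 lists five diagnoses under it: concealed Brugada, early repolarisation syndrome, idiopathic VF, Purkinje-related arrhythmic syndrome and concealed pre-excitation.

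The sample-size inputs in the same paragraph are narrower. The starting point is "Historical data report 20 to 34% sensitivity for 24-hour Holter for detection of the Brugada ECG pattern in patients with concealed Brugada syndrome". The calculation then proceeds "Assuming 25% sensitivity for 24-hour Holter and 60% for prolonged ambulatory ECG recordings beyond 24 hours". It adds an overlap, four fifths of the Holter-positive cases also being found on the longer recording, and arrives at 35 patients for 90% power at the 5% level. The paragraph ends with a recruitment target of 50 that names no diagnosis.

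The primary outcome in section 3.4 that corresponds to this test is the yield of extended monitoring "to detect the Brugada ECG pattern in patients with concealed Brugada syndrome, using neural networks 1 and 2". Idiopathic VF, another Group B diagnosis, has its own primary outcome in section 3.4 and its own 50-patient calculation in section 7.

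**The concern.** Sensitivity is defined only among people who have the condition. The 25% and 60% are sensitivities for the Brugada pattern in concealed Brugada, so the test they size should be run in those patients. Section 7 instead names a set in which four of the five diagnoses are something else.

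If the test is run on the set as named, two things change. Patients without Brugada who are negative on both recordings enlarge the denominator and pull the estimated gain down. A Brugada call made only on the longer recording of such a patient, whether a new diagnosis or a false positive, could enter as a prolonged-only discordant pair and push the gain up. Either way, the reported figure no longer estimates the quantity that section 7 assumes and section 3.4 asks for.

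**Working it through.** **Inputs (section 7).** Holter 25%, prolonged 60%, 80% of Holter-positive cases also found on prolonged recording, power 90%, level 5%. Sidedness is not stated for this test; two-sided is used.

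**1. Cells for concealed Brugada.**
- Both positive: 0.80 × 0.25 = 0.20
- Holter only: 0.25 − 0.20 = 0.05
- Prolonged only: 0.60 − 0.20 = 0.40
- Discordant share: p = 0.45; difference: d = 0.40 − 0.05 = 0.35

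**2. The plan's own figure.** n = (z₀.₉₇₅√p + z₀.₉₀√(p − d²))² / d² = (1.960 × 0.671 + 1.282 × 0.572)² / 0.1225 = 34.2, so 35. The stated figure reproduces from the concealed Brugada inputs. Exact McNemar power is 89.2% with 35 such patients and 97.7% with 50.

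**3. All of Group B tested: 50 concealed Brugada plus 50 others, negative on both recordings.** Expected discordant pairs are still 0.40 × 50 = 20 prolonged-only and 0.05 × 50 = 2.5 Holter-only. The gain becomes (20 − 2.5)/100 = 17.5 points, against (20 − 2.5)/50 = 35 points in concealed Brugada alone. McNemar's test uses only discordant pairs, so exact power hardly moves, from 97.7% to 97.4%.

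**4. Calls in the other patients.** If a share q of the 50 others has a prolonged-only call, the gain is (17.5 + 50q)/100:
- q = 0: 17.5 points
- q = 4%: 19.5 points (4% is section 7's own assumed extra-case rate in idiopathic VF, Brugada and long QT together)
- q = 10% (assumed): 22.5 points
- q = 20% (assumed): 27.5 points

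The result therefore depends on a rate that is not part of any sensitivity.

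The test itself can also be affected. Take 50 patients, half with concealed Brugada, and no true gain in them (5% discordant each way). The prolonged-only share is 0.5 × 0.05 + 0.5q and the Holter-only share is 0.025. The exact test then favours prolonged monitoring 1.3% of the time at q = 5%, 6% at q = 10% and 30% at q = 20%, against a nominal 2.5% on that side. Both the mix and q are assumptions.

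**5. The 50 are themselves a mix.** Let f be the share with concealed Brugada (assumed), the rest having no detections. Both discordant cells scale by f.

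| f | Concealed Brugada of 50 | Gain (points) | Power, normal approx. | Power, exact |
|---|---|---|---|---|
| 1.0 | 50 | 35 | 97.9% | 97.7% |
| 0.8 | 40 | 28 | 93.5% | 93.3% |
| 0.7 | 35 | 24.5 | 89.5% | 88.7% |
| 0.5 | 25 | 17.5 | 75.7% | 71.4% |
| 0.2 | 10 | 7 | 37.5% | 14.3% |

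Power drops below 90% once fewer than about 35 or 36 of the 50 have concealed Brugada.

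**The case against.** The strongest reply is that the 50 are concealed Brugada patients on any natural reading. After the sentence naming the test, everything in that paragraph is about Brugada, and idiopathic VF receives a separate 50 in the next calculation. Leaving aside the 100 patients with other inherited conditions, 50 healthy volunteers, 50 manifest Brugada, 50 concealed Brugada and 50 idiopathic VF add to the 200 of section 3.1. On that reading no power is lost. This stands, and it rules out a flat statement that the test is diluted or underpowered. It does not settle the matter, because section 3.1 also says "We will be aiming for an approximately even distribution of participants to be recruited to each group". That gives about 200/3 ≈ 67 in Group B, which does not fit 50 + 50 = 100, so the make-up of the 50 remains open.

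A reader might also infer that the plan counts detections in patients without Brugada as benefit. The documents do not say so. No section defines a detection for this test, and the section on applying the ECG AI (section 3.3) runs the algorithms on all of Group B to determine yield without saying that those calls enter McNemar's test. It is a possible consequence of the wording only. In idiopathic VF an extra Brugada detection is something the study is looking for, so it cannot be presumed false.

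Nor are all primary outcomes specific to concealed Brugada: idiopathic VF yield is primary too. Only the outcome matching this test is.

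Lastly, analysis sets are often left to a statistical analysis plan. Here the protocol does state a population, and it disagrees with the inputs beside it. That is a conflict in the text, not a detail deferred.

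**Conclusion.** The point holds as a mismatch of populations. Section 7 names a five-diagnosis set for a test whose inputs, N of 35 and corresponding outcome belong to concealed Brugada. Run as named, the paired difference is not a difference in sensitivity. With 50 concealed Brugada patients and 50 others without detections, the expected gain is 17.5 points instead of 35, while exact power stays at about 97%.

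A material loss of power, such as 71% when half of the 50 have concealed Brugada, rests on an assumed mix that the protocol neither states nor excludes. Inflation by Brugada calls in other patients is likewise possible but not written into the plan, and its size depends on assumed call rates. The mismatch should be corrected; it does not undermine the sample-size calculation for concealed Brugada.

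**What to change.** In section 7, name participants with concealed Brugada syndrome as the population for McNemar's test and the Brugada ECG pattern as the detection compared. State that the 50 to be recruited for this test are concealed Brugada patients. Report detections in the other Group B diagnoses separately as yield, including the idiopathic VF primary outcome, outside the paired test.

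The cost is a short edit to one paragraph. No extra data are needed, and the 35 and the 50 stand. The edit does not resolve how 50 concealed Brugada and 50 idiopathic VF patients fit a group of about 67; that recruitment arithmetic needs its own reconciliation.

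### Does the 87% power for the idiopathic VF cohort rest on a detection rate that the protocol's own inputs do not support?

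*Protocol*

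**What the plan says.** The idiopathic VF calculation is in the last part of section 7 (Statistics and data analysis). Its aim is put this way: "We are also seeking to identify at least one extra patient with Long QT or Brugada syndrome", by monitoring for longer than the standard 24-hour 12-lead Holter.

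Two rates from registries follow. The first is that "between 3–4% of idiopathic VF patients eventually receive a specific diagnosis of Brugada syndrome". The second is given only by comparison: "A similar proportion are diagnosed with long QT syndrome".

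The conclusion is conditional: "If extended duration monitoring can identify half of these (4%), then 50 patients will provide 87% power to detect at least one extra case". A bracket adds that the figure came from simulated binomial sampling.

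The result supports the last primary outcome in section 3.4, the yield of extended monitoring for the Brugada pattern and "LQTS manifestation in patients with idiopathic VF". The Study Summary describes the same aim as detecting a single case.

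**The concern.** The 4% stands in brackets straight after the halving, so it reads as the result of a sum. If the long QT share is taken as exactly 3–4%, the two diagnoses together make 6–8%, and half of that is 3–4%. Only the upper end is printed, and the power is worked out from that end alone. A reader could conclude that 87% is a ceiling presented as a single figure.

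A second worry is that this paragraph does not say whether the 50 are recruited or evaluable. The accuracy cohort earlier in section 7 does make that distinction: "To achieve 90 patients with some loss to follow up, I will recruit 50 healthy volunteers and 50 manifest Brugada patients".

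This is the only numerical support for the size of the idiopathic VF cohort, and it serves a primary outcome. If the true rate were 3%, the chance of finding no case would be 22% rather than 13%, and an empty result would be less surprising than the protocol suggests.

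**Working it through.** **Inputs, all from section 7.** Brugada rate 3–4%; long QT rate similar (no number given); share found by extended monitoring one half; printed detection rate 4%; n = 50; success means at least one case.

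**Formula.** The word power is used loosely here. The quantity is the probability of one or more cases, with no null hypothesis and no significance level:

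P(at least one) = 1 − (1 − r)^n

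**The protocol's figure.** With r = 0.04 and n = 50, 1 − 0.96^50 = 1 − 0.130 = 0.870. The stated 87% is reproduced, and a simulation of 1,000,000 binomial draws also gave 0.870.

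**What the halving refers to.** Half of both diagnoses together gives 4% when each is 4%: 0.5 × (4% + 4%). Half of one diagnosis alone would give 1.5–2%, for which the formula returns 53–64%. The combined reading is therefore the one that the protocol used.

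**The range if long QT is also exactly 3–4%.** The detection rate runs from 0.5 × (3% + 3%) = 3% to 0.5 × (4% + 4%) = 4%.

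| r | P(at least one), n = 50 | P(none) |
|---|---|---|
| 3% | 1 − 0.97^50 = 0.782 | 0.218 |
| 3.5% | 1 − 0.965^50 = 0.832 | 0.168 |
| 4% | 1 − 0.96^50 = 0.870 | 0.130 |

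The printed 4% is inside this range, at its upper end.

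**Is 4% necessarily the ceiling?** Only if similar means identical. As an illustration, 3.5% for Brugada and 4.5% for long QT sum to 8%, and half is 4%, with the Brugada rate at its midpoint. The document does not give the registry figures that would settle this.

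**Would 78–87% be the proper range?** It varies the registry rates but keeps the one-half fixed, and the one-half has no cited source. As an illustration, a share of 40–60% applied to 6–8% gives 0.4 × 6% = 2.4% up to 0.6 × 8% = 4.8%. The results are 1 − 0.976^50 = 0.70 and 1 − 0.952^50 = 0.91. The replacement range would show only part of the uncertainty.

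**Practice elsewhere in section 7.** The McNemar calculation cites 20 to 34% sensitivity for 24-hour Holter and then plans on 25%. That too is one value taken from a cited range, with no power range given.

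**Recruited or evaluable.** The sentence is correct for 50 analysed patients. If the accuracy cohort's margin (100 recruited for 90) were assumed here, 45 patients would give 1 − 0.97^45 = 0.746 to 1 − 0.96^45 = 0.841. That margin belongs to another cohort; the protocol does not state it for this one.

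**The case for a change.** The best case for the concern is about presentation. In the Holter calculation the chosen value is openly introduced as an assumption, whereas here the 4% looks like the outcome of a sum and the lower end disappears without comment. Rounding does not explain it, since the midpoint of 3.5% gives 83%. Keeping 87% would take 58 evaluable patients at 3.5% and 67 at 3%. The repair would be a single sentence, and the protocol elsewhere foresees that participants will not always wear the devices.

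Some of this stands. On the most natural reading of the long QT sentence, 4% is the favourable end, and the protocol does not say so. The arithmetic of the range is also right.

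It does not amount to an error. The sentence opens with a condition and prints the rate, the halving, the sample size and the method together. Nothing is hidden, and anyone can recompute the figure at another rate, as above. The 58 and 67 show a shortfall only against 87%, which the protocol reports as what 50 patients give and does not set as a target. Not stating a loss allowance for this cohort leaves out a detail; it does not make the stated figure wrong.

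**Conclusion.** The concern does not hold. The 87% is exactly what 50 analysed patients give at the 4% rate that the protocol states as its condition, and that rate is compatible with the registry inputs it cites. The spread of 78% to 87% reflects sensitivity to a planning assumption. It rests on reading the long QT share as exactly 3–4% and on holding the one-half fixed, and the protocol establishes neither as certain.

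The practical consequence is nil. The outcome is a descriptive yield, and the protocol attaches no hypothesis test, decision rule or minimum power to it. Even at the least favourable of these rates, the chance of at least one case is within two percentage points of the conventional 80%. Giving a range would be a matter of style; no analysis, sample size or conclusion depends on it.
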